4.1. Primary Endpoint

Time to all hospital episodes (Emergency Room or patient request for OPD) related to treatment for atrial arrhythmia.

4.2. Secondary Endpoints

1. Time to death or stroke from any cause.
2. Any complications caused by the procedure (pericardial effusion, bleeding >2 units, phrenic nerve palsy and other) or the anti-arrhythmic drug (GI disturbance, skin irritation and other).
3. All hospital episodes which result in a change in therapy for atrial arrhythmia.

5. Background/Introduction

5.1. Introduction

Developments in paroxysmal AF ablation have been monitored against the definition of any detected 30seconds of AF, which is not necessarily measure of symptom control. Hospital episodes are an objective and well established endpoint throughout the healthcare system and are more reflective of the patient's expectations. The increasing population burden of AF will need more cost effective approaches to treatment of symptoms. It is not known whether current approaches to antral pulmonary vein ablation still necessitates pulmonary vein mapping, which is a major source of to cost and complexity.

The proposed study is based on the following observations:

- i) AF ablation is well established as the most effective method for preventing recurrence.
- ii) Current methods for AF ablation are costly and complex with only a minority of the AF population having access to such procedure.

- iii) The Advance Cryoballoon is effective at producing antral PV ablation.
- iv) AF ablation has not been compared against anti-arrhythmic agents with the primary goal of reducing hospital episodes.

5.2. Study Design

AVATAR-AF is a multicentre, randomised controlled study comparing a streamlined AVATAR-protocol ablation procedure to anti-arrhythmic therapy in patients with documented paroxysmal AF who are considered to need an escalation of therapy. A secondary control arm will also compare the AVATAR-protocol to conventional AF ablation. 321 patients who are on no prior anti-arrhythmic, ‘pill-in-pocket’ or taking regular anti-arrhythmics will be randomised in a 1:1:1 manner to a treatment strategy of either AVATAR-protocol ablation, anti-arrhythmic therapy or conventional AF ablation and followed-up for 1 year.

5.3. Treatment Groups

- Arm 1: AVATAR-AF Ablation Protocol
- Arm 2: Conventional AF Ablation
- Arm 3: Anti-arrhythmic therapy

5.4. Study Population

The AVATAR-AF study is recruiting patients between the ages of 18 and 80 with documented paroxysmal atrial fibrillation including modification or initiation of anti-arrhythmic agent required for symptom control.

In order to be eligible for the study the patient must not have any of the following:

- Contraindication to catheter ablation
- No carer to enable daycare discharge
- Documented Arrhythmias other than AF unless they have had curative ablation (e.g. for atrial flutter)
- No documentation of sinus rhythm within 3 months
- Valvular or coronary heart disease needing regular follow up
- EF <45% or moderate/severe LV dysfunction(determined by Echocardiogram in the last 6 months)
- Active gastrointestinal disease precluding anticoagulation or trans-oesophageal echocardiogram

- Renal failure with creatinine $>200 \mu\text{mol/L}$ or on dialysis
- Active fever or infection
- Life expectancy shorter than the trial
- Allergy to contrast
- Severe cerebrovascular disease
- Bleeding or clotting disorders or inability to receive heparin
- Uncontrolled diabetes (HbA1c $\geq 73 \text{ mmol/mol}$ or HbA1c $\leq 64 \text{ mmol/mol}$ and Fasting Blood Glucose $\geq 9.2 \text{ mmol/L}$) (shown in the last six months without evidence of being brought under control)*
- Serum Potassium [K+] $<3.5 \text{ mmol/L}$ or $>5.0 \text{ mmol/L}$ (shown in the last six months without evidence of being brought under control)
- Malignancy needing surgery, chemotherapy or radiotherapy
- Pregnancy or women of child-bearing potential not using a highly effective method of contraception **
- Must not have previous (4 weeks prior to screening) or current participation in another clinical trial with an investigational drug or investigational device
- Unable to give informed consent
- Uncontrolled thyroid disease defined as abnormal thyroid function tests causing cardiac manifestations within the last 6mths
- Unable to attend follow up visits

* A fasting blood glucose must have been done within the last 6mths confirming that blood glucose under control. If no blood test result available, a new fasting blood glucose sample will be taken from all consented potential participants at screening to exclude uncontrolled diabetes, defined as:

- HbA1c $\geq 73 \text{ mmol/mol}$ or
- HbA1c $\leq 64 \text{ mmol/mol}$ and Fasting Blood Glucose $\geq 9.2 \text{ mmol/L}$

** Women of child-bearing potential not using a highly effective method of contraception must undergo a pregnancy test. Acceptable methods of contraception include the following:

- Barrier type devices (e.g. female condom, diaphragm and contraceptive sponge) used ONLY in combination with a spermicide.
- Intra-uterine devices.
- Oral contraceptive agents started at least 90 days before start of study.
- Depo-Provera (medroxyprogesterone acetate).
- Levonorgestrel implants.
- Naturally or surgically sterile (amenorrheic for at least 1 year and no record of child birth for naturally sterile persons).
- Male partner is sterile and is the only sexual partner

At the screening visit, the patient will be examined to ensure that none of the exclusion criteria are met. Their general health will be assessed in a physical examination and recording of vital signs. The patient's medical and medication history will also be recorded. A fasting blood sample will also be taken to exclude patients with uncontrolled diabetes or [K+] and serum creatinine outside acceptable safety. A blood test result within 6 months is acceptable. Any blood test result taken more than 6 months prior to randomisation will need to be repeated. A copy of the blood results must be filed in the patient notes. Any other routine clinical tests should be performed as per local practice.

If the patient does not meet any of the exclusion criteria and no additional complications are encountered during the screening process then once written, informed consent has been received the patient is eligible for randomisation.

5.5. Sample Size

In this time-to-event study of hospital episodes, required sample numbers have been estimated using the log-rank test under the Freedman method based on the occurrence of first event during the 12-month follow-up period. The null hypothesis is that there is no difference in the distributions. Adopting a conservative approach, an initial two-sided alpha of 0.05 is chosen, given the need to allow for the inherent multiple testing between the three arms of the study, the conservative Bonferroni correction is applied and the alpha value used in the power calculations is reduced to 0.025.

Estimating the proportion experiencing a hospital episode in the follow-up period in the anti-arrhythmic arm as 0.63 and the corresponding proportion in the AVATAR ablation arm as 0.40, assuming the occurrence of 103 events, with 100 evaluable patients in each of the two treatment arms yields a power of 0.80. A similar power is obtained for the comparison of the AVATAR ablation arm (0.40) and the conventional AF ablation arm (0.20).

A sensitivity analysis indicates that these sample size estimates are reasonable. It is anticipated that the loss to follow-up will be small, approximately 7%. Consequently, 321 patients will be randomised in a 1:1:1 manner to a treatment strategy of either AVATAR protocol ablation, anti-arrhythmic therapy or conventional AF ablation and followed-up for 1 year.

5.6. Schedule of Time and Events

In the 4 week period (28 days \pm 7days) between Randomisation and 1st Intervention, there will be no change to the patient's arrhythmia treatment: the treatment which the patient has been

randomised to will only occur on the date of 1st Intervention. All three treatment arms will follow the same scheduling protocol regardless of intervention.

1st Intervention will be considered baseline, all patient returning for follow-up 1 year \pm 14 days after this date. At this visit, all patients will undergo the following assessments:

- Physical Examination

- Vital signs

- Concomitant medications

- ECG

[figure not shown]
- 24 hour holter monitor tape

- EQ5D quality of life questionnaire

- Adverse Events

- Study Endpoints

- Atrial Fibrillation Effect on QualiTy of life (AFEQT) patient questionnaire

PROCEDURE	VISIT (Month)					
	SCREENING (M-0.5 \pm 14d)	1 ST INTERVENTION (M0 \pm 7 d)	WK4 REVIEW (M1 \pm 7d)	WK8 REVIEW (M2 \pm 7d)	WK12 REVIEW (M3 \pm 14d)	EOS (M12 \pm 14d)
Obtain Informed Consent	X					
Eligibility Criteria	X					
Vital Signs	X				X	X
Physical Examination	X				X	X
Medical History						
Assessment	X				X	X
Concomitant Medications	X				X	X
Fasting Blood Sample	X					
Quality of Life Questionnaire	X					X
Allocate 1 ST Intervention date	X					
Randomisation *	X					
Initiate 1 ST Intervention		X				
Allocate possible ablation 're-do' date **/†		X				
Review anti-arrhythmic medication †			X	X		
Post-ablation symptoms review **/†				X	X	
Enter Discharge Protocol					X	
Electrocardiogram						X
24-Hour Holter monitor tape						X
Echocardiogram	X					
Adverse Events		X	X	X	X	X
Study Endpoints			X	X	X	X
AFEQT patient questionnaire	X					X

* = Randomisation date to be scheduled 28d \pm 7 d from allocation of 1ST Intervention date

** = AVATAR-protocol ablation arm patients only

† = Anti-arrhythmic therapy arm patients only

^ = Conventional ablation arm patients

5.7. Randomisation

Eligible patients who have given written, informed consent and who meet all the inclusion criteria and no exclusion criteria will undergo 1:1:1 randomisation to an un-blinded treatment of either AVATAR-protocol AF Ablation, medical anti-arrhythmic therapy or conventional AF ablation. Randomisation will be performed electronically using the InForm electronic data capture system and will be stratified by site.

From the date of randomisation, the 1st Intervention date (ablation or anti-arrhythmic medication change) must occur 28 days \pm 7days after this, therefore an ablation procedure date will be identified according to local EP catheter lab availability for each consenting, eligible

patient and randomisation of the patient will then be scheduled for 28 days \pm 7 days from this available date.

The patient may be withdrawn from any AF ablation treatment by the Investigator if any safety concerns arise during the period between randomisation and the ablation which make the patient an unsuitable candidate for the procedure. The patient will then be withdrawn from the study.

6. Analysis Set

All treatment evaluation will be performed on the principle of intention to treat (ITT) with additional per-protocol analyses ran alongside if defined (see Section 8). The per-protocol analysis set will consist of patients who received treatment originally allocated.

A sensitivity analysis will also be performed excluding patients who are withdrawn from the study between randomisation and start of treatment / 1st intervention. Any subjects that have withdrawn during this period will still be required to attend the end-of-study follow-up visit.

7. Variables of Analysis

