8.3 Crossover between therapies

Following the week 12 visit, a patient from any group, the Investigator may initiate further drug therapy or schedule a standard ablation procedure for the patient. However, the following are required;

- i) *Ablation Arms (Conventional and AVATAR-AF):* Can start anti-arrhythmic drugs or further redo-ablation if there is ECG/Holter documentation of recurrent AF/AT
- ii) *Drug Therapy Arm:* May receive ablation therapy if failed one anti-arrhythmic at maximum standard dose or two anti-arrhythmic agents at sub-maximal dose or due to side effects.
- iii) *New tachycardia documented that needs treatment (VT/AVNRT/AVRT).* The patient is withdrawn from the study

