7.2. Secondary Endpoint Variables

1. Time from 1st intervention to death or stroke from any cause.
2. Number of and time from 1st intervention to any of the following complications caused by:
 - Pericardial Effusion
 - Vascular Bleeding (>2 units)
 - Phrenic Nerve Palsy
 - PV Stenosis
 - Drug side-effects (including GI disturbance, skin irritation and other)
 - Other

3. Number of and time from 1st intervention to any hospital episodes which result in a change in therapy for atrial arrhythmia.

Information about trial adverse events will be collected from randomisation until the end of the trial.

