8.4. Safety Variable Analysis

Adverse events will be summarised by treatment and severity. A separate table summarising adverse events and their relationship to study treatment will also be produced.

Serious adverse events will be listed and summarised by site, category and treatment. A separate table summarising serious adverse events and their relationship to study treatment will also be produced.

All safety variables will be summarized in the form of frequency tables for categorical variables or descriptive statistics for continuous variables. Quality-of-Life (QoL) questionnaire results will be summarised by Health State Score. Atrial Fibrillation Effect on QualiTy-of-life (AFEQT) questionnaire results will be summarised by both overall AFEQT score and subscale score derived using the formulae stated within the AFEQT Questionnaire Instruction and Scoring Manual

REFERENCES

If it is deemed appropriate, treatment effect will be assessed via t-test for continuous variables and Chi-square test or Fisher exact test for categorical variables (with the appropriate generalized linear model being used). Models containing one or more of the following covariates may also be assessed if deemed necessary: site, weight, hypertension, number of anti-arrhythmics taken by patient prior to 1st intervention. A p-value of 0.025 or less will be considered significant. Any testing for treatment effect will be carried out between AVATAR-AF Ablation and the Anti-Arrhythmic drug treatment arm in order to investigate the primary objective. The secondary objective will be assessed by testing AVATAR-AF Ablation against the Conventional Ablation arm.

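### The plan defines no harms analysis by treatment received and no crossover rule for harms, which dilutes the AVATAR-versus-drug difference in procedural complications

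*SAP*

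**What the plan says.** **Analysis sets (SAP 6).** The governing sentence begins "All treatment evaluation will be performed on the principle of intention to treat (ITT" and adds per-protocol analyses where Section 8 defines them. Two supplements follow. The first is the per-protocol set: "The per-protocol analysis set will consist of patients who received treatment originally allocated". The second is "A sensitivity analysis will also be performed excluding patients who are withdrawn from the study between randomisation and start of treatment".

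**Complications (SAP 7.2 and 8.3).** The endpoint is defined as "Number of and time from 1st intervention to any of the following complications caused by" a list that covers both procedural events and drug side effects. SAP 8.3 analyses it by Kaplan-Meier, log-rank and proportional hazards, with a per-protocol analysis in addition.

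**Adverse events (SAP 7.2 and 8.4).** "Information about trial adverse events will be collected from randomisation until the end of the trial". In the analysis, "Adverse events will be summarised by treatment and severity". SAP 8.4 does not say whether treatment means assigned or received, and it names no safety set.

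**Crossover (Protocol 8.3).** After the week 12 visit a drug-arm patient "May receive ablation therapy if failed one anti-arrhythmic at maximum standard dose", or on the other grounds listed there. Ablation-arm patients may start anti-arrhythmic drugs or have a further redo if recurrence is documented. The only rule for handling a switch, in Protocol 11.2, is censoring, and it is written for the primary outcome.

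**The concern.** A harms summary should let the reader see which treatment an adverse effect followed. Here a pericardial effusion after an ablation given to a drug-arm patient in, say, month 7 would be an event of the anti-arrhythmic arm. It would enter the log-rank and Cox comparisons in Tables 5.5 and 5.6, the adverse event tables 7.1 to 7.4, and the SAP 8.8 plot of procedural complications by arm. A drug side effect in an ablation patient who later starts a drug would count in the ablation arm.

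The causality scale in Protocol 10.4 does not separate the two. Each grade refers to anti-arrhythmic or ablative therapy together, so the effusion could be graded as definitely related and still stand in the anti-arrhythmic row of Tables 7.2 and 7.4.

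At stake is the contrast in procedural complications between AVATAR ablation and drugs. It is a cost of ablation that has to be weighed against any gain on the primary endpoint.

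**Working it through.** The plan states no figure on this point, so there is none to reproduce. The check has two parts.

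**1. Does any planned analysis separate events after a crossover?**

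- *ITT tables:* no, by construction.
- *Per-protocol set:* no. A drug-arm patient who started the agreed drug and was ablated later did receive the allocated treatment. The definition has no exclusion or censoring at a later switch.
- *Sensitivity analysis:* no. It removes only patients withdrawn before 1st intervention.
- *SAP 8.4:* it sets no rule of its own, so the ITT default in SAP 6 is the natural reading. At best the grouping is unstated.
- *Procedure tables:* Tables 6.1 to 6.3 cover the two ablation arms. Tables 6.4 and 6.5 cover the drugs assigned and the week 4 and week 8 reviews. None counts ablations given to drug-arm patients, so a per-procedure rate has no planned denominator.

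**2. How large is the dilution?**

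Inputs:
- 107 patients per arm: 321/3 (Protocol 11.1, SAP 5.5).
- q, the procedural complication rate per ablation: not in the documents; assumed 2% to 8%.
- x, the share of the drug arm ablated after crossover: not in the documents; assumed 10% to 40%.
- r, the share of ablation patients with a redo: not in the documents; taken as 0, then as an assumed 20%.

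With one ablation per ablation-arm patient and the same q for a crossover ablation:
- difference without crossover = q
- difference by assignment = q − qx = q(1 − x)
- proportional loss = x, whatever q is
- procedural events counted in the drug arm = 107 × q × x

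Each cell gives the by-assignment difference in percentage points, then the events counted in the drug arm:

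| q | x = 10% | x = 20% | x = 40% |
|---|---|---|---|
| 2% | 1.8; 0.21 | 1.6; 0.43 | 1.2; 0.86 |
| 5% | 4.5; 0.54 | 4.0; 1.07 | 3.0; 2.14 |
| 8% | 7.2; 0.86 | 6.4; 1.71 | 4.8; 3.42 |

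For example, q = 5% and x = 20% give 5.0 × (1 − 0.20) = 4.0 points instead of 5.0, with 107 × 0.05 × 0.20 = 1.07 events in the drug arm.

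With redos, the ablation arm expects q(1 + r) complications per patient and the difference by assignment is q(1 + r − x). The proportional loss is x/(1 + r). At r = 20% it is 0.10/1.2 = 8.3%, 0.20/1.2 = 16.7% and 0.40/1.2 = 33.3%.

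These formulas describe procedural complications only. The tests in Tables 5.5 and 5.6 pool procedural and drug complications as time to event, and switching runs both ways. The figures are therefore not the bias of those tests, whose net direction the documents do not settle.

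**The case against.** The best defence is that the trial randomises to a treatment strategy. A permitted later ablation is part of a drug-first strategy, and its complications belong to that strategy. This stands: the by-assignment comparison is valid and should stay. It does not tell the reader how often the procedure causes harm relative to drugs, and no planned table does that cleanly.

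Four stronger readings are tempting, and the documents do not support them.

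- *Safety is analysed only by assigned arm.* This ignores the per-protocol analysis of complications, the sensitivity analysis and the open wording of SAP 8.4. The supplements exist; they do not deal with later switchers.
- *Adverse events during the wait of about 28 days hide procedural harm.* The complications endpoint is timed from 1st intervention, so they cannot enter it. In the general tables they have the same expectation in every arm: patients are randomised, the wait is the same, and arrhythmia treatment is unchanged (Protocol 6, SAP 5.6). They add noise, not a difference.
- *The day-case safety comparison is compromised.* Protocol 6.3 names complication rates as an interest for conventional versus AVATAR ablation. Drug-arm crossover changes neither ablation arm.
- *The loss can be read off the planning rates.* Taking 63% of 107 (67.4 patients) with a hospital episode and supposing that 25% to 50% of them are ablated gives 16.9 to 33.7 patients, a loss of 16% to 31%. The 25% to 50% is an assumption, a hospital episode is not the crossover criterion in Protocol 8.3, and redos are left out.

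It is also fair to say that single events can be traced: Table 5.4 lists date, cause and relation for each complication, and Table 7.3 does much the same for serious events. The listings do not alter the summaries, tests or plot.

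**Conclusion.** The gap is real but limited. The SAP has no treatment-received analysis of harms and no crossover rule for complications or adverse events, and its per-protocol set does not remove later switchers. By-assignment results remain valid for comparing strategies. As a measure of procedural harm, the AVATAR-versus-drug difference is diluted by about x, or x/(1 + r) with redos: 10% to 40% for x of 10% to 40% without redos, and 8% to 33% if 20% of ablation patients have a redo.

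This rests on assumed crossover and redo shares and on an equal complication rate for index, redo and crossover ablations. In absolute terms it is about 0.2 to 3.4 events in 107 patients over the assumed ranges. That is a small number, but complications are few.

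A reader should not infer that the ablation arms' own rates, or AVATAR versus conventional, are biased by drug-arm crossover.

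**What to change.** In SAP 8.4, state that the main harms tables are by assigned arm and keep them. Add, labelled as non-randomised:

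- **(a)** complication, adverse event and serious adverse event tables by treatment received, with each patient's time split at first crossover;
- **(b)** procedural complications per procedure performed, shown separately for index, redo and crossover ablations, with the number of crossover ablations reported as the denominator for the last.

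Item (b) has a further use: a redo in the AVATAR arm involves PV mapping (Protocol 6.1.1 and 6.4), so separating it keeps its complications apart from those of the streamlined index procedure.

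Showing adverse events before 1st intervention in their own column is an optional matter of presentation, not a bias correction.

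The cost is a few tables. The dates should already be in the data, since Tables 5.4, 5.7 and 7.3 call for dates of complications, changes of therapy and serious events. The drawback is that patients who cross over are selected by how they fared on drugs, and the crossover denominator may be small: 107 × 0.10 = 10.7 to 107 × 0.40 = 42.8 patients under the assumed range. The added tables should therefore be descriptive.

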7.1. Primary Endpoint Variable

Time from 1st intervention to any hospital episodes (Emergency Room or patient request for OPD) related to treatment for atrial arrhythmia that has been formally adjudicated by an independent committee as a primary endpoint. Failure to enter discharge protocol at the Week 12 Review will also result in the primary endpoint being met.

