6.1.1 Review 1 (8 weeks ± 7 days post-ablation)

The patient is first reviewed 8 weeks ± 7 days post ablation. If asymptomatic for palpitations, weekly improvement or not possible to assess in time scale then the patient is entered into discharge protocol at 12 weeks ± 14days.

If there are ongoing symptoms then the redo procedure (as scheduled post 1st Intervention ablation) will be performed which will be a conventional PVI using radiofrequency thermocool catheter and PV mapping catheter or according to local practice. A daycare approach is taken again as per first procedure and the patient is reviewed at 12 weeks ± 7days and if stable enters Discharge protocol at 12 weeks ± 14days.

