6.2 Anti-arrhythmic therapy

The anti-arrhythmic agent or the change in dose that was discussed with the patient selected as the next line of treatment at the initial screening visit is initiated at the 1st Intervention date. The anti-arrhythmic treatment is chosen should be done in accordance with local practice and guidelines.

The patient will undergo 2 reviews prior to entering the Discharge protocol.

- ***Review 1 (4 weeks post-1st Intervention)***
- ***Review 2 (8 weeks post-1st Intervention)***

At each review, the patient can be left unchanged, have an increase in drug dose or change of agent as required. Review 1 at 4 weeks post 1st intervention can take place as a telephone follow up followed by a clinic visit if required. Following the 2 reviews, the patient enters the Discharge protocol at 12 weeks ± 14days.

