7 ASSESSMENT AND FOLLOW-UP

7.1 Discharge Protocol

Patients from the all therapy arms will enter the Discharge protocol 12 weeks \pm 14days post-1st Intervention providing no ongoing symptoms are presented before this.

Patients will be given the centre's Research Nurse contact details and are able to request an unscheduled visit if they experience recurrent symptoms and need hospital review. A blinded research Nurse or designee will contact the patient by telephone every 3 months to ensure that no endpoints have occurred.

The patient will be advised that the blinded research Nurse or designee making the phone call will not know which treatment they have received and the patient will be given a copy of the questions that they will be asked.

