7.1.1 Patients unable to enter the Discharge Protocol

Patients not able to enter the discharge protocol at 12 weeks will have necessary advice (further OPD, procedure) which will be a primary endpoint. The date of the endpoint will be the date of the subsequent event. These patients will be followed up at their usual study visits at M6, M9 and Final visit.

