8.4 Endpoint Adjudication

The endpoint adjudication will be done by an independent Endpoint Adjudication Committee (EAC). The EAC will centrally review and classify suspected outcome events, verifying whether they meet protocol definitions. Any hospital episodes (Emergency Room or outpatient) related to treatment for atrial arrhythmia, Stroke or Death from any cause, Any complications caused by the procedure (pericardial effusion, bleeding >2 units, phrenic nerve palsy and other) or the anti-arrhythmic drug (GI disturbance, skin irritation and other), All hospital episodes which result in a change in therapy for atrial arrhythmia.

Any attendance to hospital or specialist cardiac clinic will require the documentation of a discharge letter or clinic letter for primary endpoint adjudication.

Definitions of study endpoints: see Appendix 2

9 Patient visit schedule

PROCEDURE	VISIT (Month)					
	SCREENING (M-0.5 \pm 14d)	1 ST INTERVENTION (M0 \pm 7d)	WK4 REVIEW (M1 \pm 7d)	WK8 REVIEW (M2 \pm 7d)	WK12 REVIEW (M3 \pm 14d)	EOS (M12 \pm 14d)
Obtain Informed Consent	X					
Eligibility Criteria	X					
Vital Signs	X				X	X
Physical Examination	X				X	X
Medical History Assessment	X				X	X
Concomitant Medications	X				X	X
Fasting Blood Sample	X					
Quality of Life Questionnaire	X					X
Allocate 1 ST Intervention date	X					
Randomisation *	X					
Initiate 1 ST Intervention		X				
Allocate possible ablation 're-do' date ** [†]		X				
Review anti-arrhythmic medication			X	X		
Post-ablation symptoms review ** [†]				X	X	
Enter Discharge Protocol					X	
Electrocardiogram						X
24-Hour Holter monitor tape						X
Echocardiogram	X					
Adverse Events		X	X	X	X	X
Study Endpoints			X	X	X	X
AFEQT patient questionnaire	X					X

* = Randomisation date to be scheduled 28d \pm 7d from allocation of 1ST Intervention date

** = AVATAR-protocol ablation arm patients only

† = Anti-arrhythmic therapy arm patients only

^ = Conventional ablation arm patients

10 Safety Reporting

Information about trial adverse events will be collected from randomisation until the end of the trial

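### Week-12 non-entry to the discharge protocol is a primary event, but the entry rule conflicts between sections and partly between arms, and adjudication and dating of this route are not settled

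*SAP*

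**What the plan says.** Both documents make week-12 non-entry a primary event.

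- SAP 7.1: "Failure to enter discharge protocol at the Week 12 Review will also result in the primary endpoint being met".
- Protocol 7.1.1: "Patients not able to enter the discharge protocol at 12 weeks will have necessary advice (further OPD, procedure) which will be a primary endpoint". On timing it adds: "The date of the endpoint will be the date of the subsequent event". SAP 7.1 gives no date for this route.

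The rule for entering is stated in several places.

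- Protocol 7.1, all arms: entry at 12 weeks, "providing no ongoing symptoms are presented before this".
- Protocol 6.1.1, AVATAR arm at week 8: "If asymptomatic for palpitations, weekly improvement or not possible to assess in time scale then the patient is entered into discharge protocol". Section 6.3.1 repeats this for conventional ablation. Patients with ongoing symptoms go to redo.
- After redo, 6.1.1 admits AVATAR patients who are stable, a term it does not define. Section 6.3.1 gives no post-redo rule.
- Protocol 6.2, drug arm: "Following the 2 reviews, the patient enters the Discharge protocol". No symptom condition is attached.
- Protocol 6.5, all arms: suitability is reviewed at week 12, with no criterion.

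On adjudication, the first sentence of SAP 7.1 requires formal committee adjudication of hospital episodes, and the non-entry sentence follows separately. Protocol 8.4 says: "The EAC will centrally review and classify suspected outcome events, verifying whether they meet protocol definitions". The list after it includes emergency and outpatient episodes for atrial arrhythmia but does not name non-entry.

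**The concern.** Whoever decides that a patient does not enter the discharge protocol is in effect deciding a primary outcome. If the sections disagree on the criterion, two sites following different sections can record different outcomes for the same patient. Where the rules also differ by arm, the endpoint differs by arm.

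The decision is exposed to knowledge of treatment. Allocation is un-blinded (Protocol 5.4), and nothing describes masking of the week-12 review. The masked telephone calls (Protocol 7.1, 7.2) cover only later follow-up. The introduction to the protocol justifies the endpoint by the objectivity of hospital attendance, whereas this route turns on symptoms. At stake is the comparability of the primary event in both planned comparisons, chiefly AVATAR against drugs.

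**Working it through.** **1. The entry rules side by side.** Non-entry is an event under SAP 7.1. Reading each section literally:

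| Patient | Drug arm (6.2) | AVATAR (6.1.1) | Conventional (6.3.1) | All arms (7.1) |
|---|---|---|---|---|
| No symptoms | enters | enters | enters | enters |
| Symptomatic, improving weekly | enters | enters | enters | does not enter: event |
| Symptoms persist, not improving | enters, no event | redo; enters if stable, otherwise event | redo; no rule afterwards | does not enter: event |
| Not assessable at week 8 | enters | enters | enters | depends on symptoms presented |

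Two separate conflicts follow.

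- *Between sections:* row 2 is a success throughout section 6 and a failure under 7.1, in any arm.
- *Between arms within section 6:* row 3 is no event in the drug arm but a possible event in the AVATAR arm. Between the two ablation arms, the only gap is the missing post-redo rule.

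Nothing says whether section 6 or 7.1 prevails.

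**2. The plan's own figure.** Inputs from SAP 5.5: proportions 0.63 (drug) and 0.40 (AVATAR), 100 evaluable per arm, alpha 0.025 (taken as two-sided), Freedman method, power 0.80.

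- HR = ln(1 − 0.40)/ln(1 − 0.63) = 0.514.
- Events D = 100 × (0.63 + 0.40) = 103, as stated.
- Power = Φ(√D × (1 − HR)/(1 + HR) − z), with z = 2.241: Φ(3.260 − 2.241), about 0.846.

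The stated 0.80 is not reproduced at 0.025; alpha 0.05/3 gives 0.807. The mismatch leaves the plan slightly over-powered and has no bearing here. The baseline below is 0.846.

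**3. Illustration under no true difference.** The documents do not say how many patients the rules would classify differently. Assume that both arms share a true proportion p and that the entry rule alone lowers one arm by x. Then HR = ln(1 − p + x)/ln(1 − p), D = 100 × (2p − x), t = √D × (1 − HR)/(1 + HR), and the rejection rate is Φ(t − 2.241) + Φ(−t − 2.241).

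| x (points) | p = 0.40 | p = 0.50 | p = 0.63 |
|---|---|---|---|
| 0 | 0.025 | 0.025 | 0.025 |
| 3 | 0.040 | 0.039 | 0.040 |
| 5 | 0.068 | 0.066 | 0.069 |
| 10 | 0.225 | 0.211 | 0.221 |

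For example, with p = 0.50 and x = 10 points: HR = ln(0.60)/ln(0.50) = 0.737, D = 90, t = 1.436, rejection rate 0.211.

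**4. Direction under the planned effect.** Same formula as step 2, with x again assumed.

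- Unconditional entry lowers the drug arm: 0.58 v 0.40 gives HR 0.589, power 0.63; 0.53 v 0.40 gives HR 0.677, power 0.35.
- Lenient entry lowers the AVATAR arm: 0.63 v 0.35 gives HR 0.433, power 0.95; 0.63 v 0.30 gives HR 0.359, power 0.99.

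The shift can work for or against AVATAR.

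**The case against.** **Section 7.1 already gives one rule for all arms.** Sections 6.1.1 and 6.3.1 can be read as week-8 routing and 6.2 as scheduling, while 6.5 and 7.1.1 apply to everyone. This has force: the arm difference exists only because section 6 conflicts with 7.1. But section 6 says who enters at week 12, and nothing subordinates it to 7.1.

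**A reader might infer that an improving but symptomatic patient fails in one arm and succeeds in another.** The documents do not support that. Section 6 admits such a patient in every arm and 7.1 excludes the same patient in every arm. The split by arm concerns persisting, non-improving symptoms.

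**A reader might infer that this route bypasses the committee and that the investigator alone creates the event.** That is too strong. Protocol 8.4 covers suspected outcome events generally, names outpatient episodes and asks for a letter for any hospital or specialist cardiac clinic attendance. A further visit or procedure under 7.1.1 could fit. SAP Table 4.1 also places discharge-protocol status beside the adjudication reason and endpoint status. Adjudication may well be intended, but no text expressly requires it. It would not cure the conflict either, because the committee verifies against protocol definitions and those disagree.

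**A reader might attach a large, definite loss of power or a known bias.** The documents give no basis for the share reclassified. Counting improving patients in one arm only would need a site to apply 7.1 to one arm and section 6 to the other, which nothing prescribes.

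**Conclusion.** The point stands as a contradiction inside the primary endpoint, not as missing detail. Non-entry is an event in both documents, the entry rules cannot all be followed, and for persisting symptoms section 6 treats the drug and AVATAR arms differently. Adjudication of this route is unclear rather than excluded, and its date appears only in the protocol.

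The direction of bias is not fixed and its size cannot be derived from the documents. The figure of 0.21–0.23 in place of 0.025 rests on an assumed 10-point gap; at 3 points the rate is about 0.04. It also assumes the Freedman approximation, 100 evaluable patients per arm and proportional hazards. It shows why the wording matters and does not predict what will happen. The passages should be reconciled before the primary analysis.

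**What to change.** 1. For endpoint purposes, state one week-12 event, identical in all arms, in Protocol 7.1/7.1.1 and SAP 7.1. Build it on the existing 7.1.1 wording: a further outpatient visit or procedure for atrial arrhythmia arranged at the week-12 review. Do not add change of therapy. Protocol 8.3 sets arm-specific conditions for that, and drug adjustment is the drug arm's own treatment.
2. Reconcile Protocol 6.1.1, 6.2, 6.3.1, 6.5 and 7.1 with that definition, including the missing post-redo statement for conventional ablation. Which clinical entry rule applies is for the investigators.
3. Put this route expressly under committee adjudication in SAP 7.1 and Protocol 8.4, judged from the week-12 letter.
4. State the same event date in both documents.
5. Add a sensitivity analysis of the primary endpoint without the week-12 component.

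The cost is wording in two documents, a few more cases for an existing committee and one extra analysis. The week-12 decision would still be taken by unmasked clinicians, which is why items 3 and 5 belong with item 1.
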